6 STATISTICAL ANALYSIS

6.1 General

The final statistical analysis will be performed as pre-specified in this SAP and the planned analyses identified in this SAP will be included in future manuscripts. Any, post-hoc, exploratory analyses completed to support planned analyses, which were not identified in this SAP, will be documented and reported in the relevant trial reports. Any results from unplanned analyses will be clearly identified in the text of the trial reports.

6.2 Pooling of Sites

The data from each participating centre will be pooled for all primary and secondary analyses.

6.3 Interim Analysis

An independent Data and Safety Monitoring Committee (DSMC) was established and a separate DSMC charter developed which includes details of the meeting schedule and stopping guidelines.

6.4 Time Points for Analysis

All final, planned, analyses identified in the protocol and in this SAP will be performed only after the last patient has completed their 2-year follow-up. In addition, no database may be locked, randomisation code unblinded, or analyses completed until this SAP has been approved other than for any pre-specified interim analyses.

6.5 Methods for Handling Withdrawals and Missing Data and Other Issues

6.5.1 Withdrawals

Patients who are randomised but withdraw before the intervention will undergo standard clinical care according to local protocols. Patients will be encouraged to allow data and samples that have been collected before withdrawal to be used in the analysis. However, if consent to use data/samples is also withdrawn, then these will be discarded.

6.5.2 Missing Data

Missing data will be identified and an effort made to return to the original medical records to obtain the data. If this is not possible and the data are missing, modelling

techniques and appropriate missing imputation methods will be considered depending on the scale and the pattern of missing data. See Section 9.2.1 for further details.

6.5.3 Data Transformations

The primary endpoint involves the occurrence or not of an event and so will not require any data transformation for the primary analyses. In the case of secondary endpoints that involve a continuous outcome, the outcome variable will be assessed to establish if a transformation, for example logarithmic, may be necessary to allow for analysis with the most appropriate statistical method. Where possible results will be presented on the original scale to aid in a clinical interpretation.

6.5.4 Multiplicity

There are no planned adjustments to the Type I error for multiple comparisons.

6.5.5 Covariate Adjustment

There are no planned covariate adjustments for the primary analysis or for other event-based outcomes. However, a secondary sensitivity analysis of the primary outcome will be performed adjusting for risk factors derived using the risk score (Section 5.4 and Section 9.1).

There will be adjustment for baseline values of continuous secondary outcomes where indicated in Section 9.2.1.

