4.2 Sample Size

The predicted occurrence of death or hospitalisation for heart failure at 2 years is 36% in the OMT group. The primary endpoint in REVIVED-BCIS2 will be measured over the entire trial duration, with a minimum follow-up duration of 2 years, thus increasing the number of events. A trial of 700 (350 in each group), with 300 patients experiencing primary outcome events, would have over 85% power to detect a hazard ratio of 0.7 (a 30% relative reduction in the hazard) at 5% significance allowing for up to 5% losses by the end of follow-up and increasing recruitment over time. For illustrative purposes this represents a reduction to 27% of patients with an event in the PCI group at two years.

The hazard ratio of 0.7 is considered clinically meaningful and in line with the magnitude of benefit observed across other treatment modalities in this population. For the major secondary endpoint of LVEF, even one-half of this sample size will provide 90% power to detect a minimum difference in LVEF of 4%, assuming a standard deviation of 11%.

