4.3 Randomisation and Blinding

Randomisation of the treatment assignment will be stratified by centre using randomly permuted blocks of varying size, with 1:1 allocation between the PCI and OMT alone arms. This will be done on a secure web-based service through the Clinical Trials Unit at LSHTM. It is recommended that index PCI be carried out as close as possible to randomisation to minimise the incidence of major adverse cardiovascular events prior to the assigned treatment.

Due to the nature of the intervention being assessed (PCI versus medical therapy) this is an open trial and patients / investigators will not be blinded to treatment assignment. However, independent personnel who are blinded to treatment assignment will centrally adjudicate all major endpoints.

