5.3 Definition of Subgroup Populations in Different Analyses

We plan to undertake a limited number of subgroup analyses for the primary endpoint. Since the subgroup analyses are secondary analyses and exploratory in nature, the trial has not been powered for these. The pre-specified subgroup analysis will be performed on the following variables using Cox proportional hazards model incorporating tests of interaction:

- Age
- The extent of coronary disease (BCIS-JS)
- Degree of LV dysfunction (% LVEF)
- Diabetes
- NYHA class
- Unprotected left main stem disease
- Presence of atrial fibrillation at baseline
- BNP/NT-pro-BNP at baseline

For analysis of BNP/NT-pro-BNP, as different assays have been used across clinical sites, values will be standardised to the upper limit of normal (ULN) for the local assay. Results will be expressed as multiples of the ULN, with subsequent analysis performed using these standardised values.

For the continuous variables of age, degree of LV dysfunction and the standardised values of the BNP/NT-pro-BNP the cutpoint for the subgroup analysis will be at the median value. For the extent of coronary disease and NYHA class two categories will be formed for the subgroup analysis. For NYHA class these will be classes I/II and III/IV, and for extent of coronary disease these will be ≤ 8 or ≥ 10 according to BCIS-JS. The remaining variables are binary.

In addition, an analysis will be undertaken according to a patients' underlying risk of the primary outcome. First, univariate Cox proportional hazards model will be used to assess the associations between each potential risk factor and the outcome. Using a forwards modelling approach, risk factors will be entered into a multivariable Cox regression model one at a time, starting with those showing the strongest association with the outcome in the univariable analyses. The final model will include all risk factors that are independently associated with the outcome, as well as an indicator variable for randomised treatment. Using this model, a risk score for the primary outcome will be calculated for each patient (assuming the patients received OMT only) and an interaction term fitted in the Cox model for the primary outcome between risk and treatment to establish if there is greater benefit of PCI according to underlying risk.

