7.1. Viability and event-free survival

A Cox proportional hazards model will be used to assess the relationship between the number of viable myocardial segments (treated as a linear effect) and the primary outcome. Multivariable Cox analyses will be used to adjust the analysis for factors including age, sex, previous hospitalisation for heart failure, presence of diabetes, ejection fraction, extent of coronary disease, presence of chronic renal failure and modality of viability testing. The interaction between viability and treatment assignment on event-free survival will then be assessed using a Cox proportional hazards model containing the following covariates: viability (treated as a linear effect), randomly assigned treatment, and their interaction, plus the aforementioned list of baseline risk factors. In secondary analyses, the extent of viability will be divided into tertiles and Kaplan-Meier curves stratified by both viability tertile and treatment assignment presented. A sensitivity analysis will be performed where viability is defined irrespective of resting dysfunction (including segments with normal function at rest and with \$25% scar on CMR or contractile reserve on DSE).

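### The unadjusted primary Cox model is valid but forgoes some power; the adjusted analysis has no fixed covariate list, and three exploratory interaction tests are weakened by median splits

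*Protocol*

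**What the plan says.** Section 6.5.5 of the main SAP says: "There are no planned covariate adjustments for the primary analysis or for other event-based outcomes". Protocol section 8.3 and SAP section 9.1 agree with this: the primary analysis is an unadjusted Cox model of time to first event, by intention to treat.

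The sample size section (SAP 4.2) plans 700 patients, and "with 300 patients experiencing primary outcome events, would have over 85% power to detect a hazard ratio of 0.7", "at 5% significance allowing for up to 5% losses by the end of follow-up".

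On allocation, SAP section 4.3 states: "Randomisation of the treatment assignment will be stratified by centre using randomly permuted blocks of varying size". Section 6.2 pools the centres, and no centre term is planned.

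One adjusted analysis of the primary outcome is planned, as a sensitivity analysis (sections 6.5.5 and 9.1). Its covariates come from the risk-score model in section 5.3: "Using a forwards modelling approach, risk factors will be entered into a multivariable Cox regression model one at a time", starting with the strongest univariable associations. No candidate list or entry threshold is given.

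For the age, LVEF and standardised BNP/NT-proBNP subgroups, section 5.3 says "the cutpoint for the subgroup analysis will be at the median value". NYHA class and jeopardy score have fixed categories and the other subgroup variables are binary. All subgroup tests are declared exploratory and unpowered.

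The Viability SAP, section 7.1, does it differently. It names covariates, among them "age, sex, previous hospitalisation for heart failure, presence of diabetes, ejection fraction, extent of coronary disease, presence of chronic renal failure", and enters viability as a linear term, with tertiles as secondary.

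**The concern.** In a Cox model, leaving out strong predictors pulls the estimated treatment hazard ratio towards 1 while its standard error hardly changes, so the test loses power. Protocol section 8.1 accepts that a smaller effect may matter clinically but says that powering for it would greatly increase the sample size and might threaten feasibility. Power that needs no extra patients is therefore worth having.

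Two related choices weaken the supporting analyses. An adjusted model whose covariates are chosen from the outcome data, with no stated candidates or stopping rule, cannot be reproduced from the text: two analysts could follow section 5.3 and fit different models. And cutting a continuous modifier at its median discards information in interaction tests that already have little.

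**Working it through.** **1. The plan's own figure.** Inputs from SAP 4.2: 300 events, hazard ratio 0.7, 5% significance (taken as two-sided), 1:1 allocation.

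- Schoenfeld: Φ(√300/2 × |ln 0.7| − 1.96) = Φ(8.660 × 0.3567 − 1.96) = Φ(1.129) = 87.1%.
- Freedman: Φ(√300 × 0.3/1.7 − 1.96) = Φ(1.097) = 86.4%.
- Events needed for 85% power: 283 (Schoenfeld) or 289 (Freedman).
- Two-year PCI risk: 1 − 0.64^0.7 = 26.8%, matching the stated 27%.

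The stated power holds for the unadjusted test.

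**2. Power forgone.** Simulated trials: 700 patients, 40 centres of unequal size, permuted blocks within centre, rising recruitment, follow-up cut at 300 events, 1,500 runs per setting. Assumed, because the documents give neither: an SD of 0.4, 0.6 or 0.8 for the baseline log-hazard score and 0.2 to 0.3 for centre. The conditional hazard ratio was set (0.688, 0.676, 0.655) so that the unadjusted one stayed near the planned 0.70.

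| SD of baseline score | Unadjusted | Stratified by centre only | Adjusted for baseline score | Both |
|---|---|---|---|---|
| 0.4 | 86.0% | 85.5% | 88.5% | 87.5% |
| 0.6 | 86.3% | 85.8% | 91.1% | 90.1% |
| 0.8 | 86.3% | 85.9% | 94.7% | 94.1% |

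Gain from adjustment: 2.5, 4.8 and 8.4 points. As a check at SD 0.6, the mean hazard ratio moves from 0.700 to 0.677 while the standard error goes from 0.1167 to 0.1169. The expected z is 0.3567/0.1167 = 3.06 unadjusted and 0.3901/0.1169 = 3.34 adjusted, so power is Φ(1.10) = 86% and Φ(1.38) = 92%, in line with the table.

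**3. Centre.** Stratifying by centre changes power by about −0.5 point. With no treatment effect (2,000 runs, SD 0.6), the unadjusted test rejects in 4.6% of trials and the stratified one in 4.8%.

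**4. Forward selection.** 700 runs with ten candidate covariates, four truly prognostic (log hazard ratios 0.35, 0.30, 0.30 and 0.20 per SD), an assumed entry rule of |z| > 1.96, and a conditional hazard ratio of 0.7.

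| Model | Power | Rejection under the null |
|---|---|---|
| Unadjusted | 82.3% | 4.9% |
| Fixed list | 88.9% | 5.4% |
| Forward selection | 89.0% | 5.1% |

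Selection costs no power and does not visibly inflate the error rate.

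**5. Median splits.** For a normally distributed modifier with a linear interaction, a median split has relative efficiency 2/π = 0.637. If the continuous test has power 80%, the split test has Φ((1.96 + 0.842) × √0.637 − 1.96) = Φ(0.275) = 61%. By the same formula 90% falls to 73%, and 50% to 35%.

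**The case against.** The case for leaving the plan alone is substantial. The unadjusted model is stated consistently in protocol and SAP, is valid, and delivers its stated power. The planned 0.70 is tied to two-year risks of 36% and 27%, so it is naturally read as a marginal hazard ratio. The unadjusted estimate also sits well beside the planned Kaplan-Meier difference at two years and needs no covariate choice or imputation. Forward selection touches only a sensitivity analysis. A median rule fixed in advance prevents data-driven cutpoints, and it affects three exploratory tests. The risk-by-treatment interaction in section 5.3 is fitted on each patient's score, with the three risk groups formed separately. All of this stands, and it limits the point to an improvement.

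Four stronger readings are tempting, and the documents do not support them:

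- **The trial is underpowered.** Reading 0.70 as a conditional hazard ratio would put unadjusted power at 83.3, 80.5 and 74.7% (85.9, 87.0 and 86.0% adjusted) for the three assumed SDs. The stated event risks point to the marginal reading, and the SDs are assumptions.
- **Omitting centre costs power or validity after centre-stratified randomisation.** The simulations show neither. A shared-frailty term was not tested.
- **Outcome-driven selection loses power.** It does not.
- **The Viability SAP list could simply be carried over.** It is introduced as a set of factors to be included, so it is not closed. It stands in a version dated December 2022, which states only that it preceded unblinding of the imaging core-laboratory results. Prior heart-failure hospitalisation is also not among the baseline variables in main SAP sections 7.2 to 7.4.

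**Conclusion.** The point holds as an inexpensive improvement to a valid plan. Three separate things are established:

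- **Primary test:** it forgoes about 2.5 to 8 points of power if the measured baseline score has an SD of 0.4 to 0.8. The documents do not give prognostic strength, so the size is conditional on that range; with weaker predictors the gain would be smaller.
- **Adjusted sensitivity analysis:** it is under-specified, because the candidates and entry rule are missing. This is a matter of reproducibility.
- **Interaction tests for age, LVEF and BNP/NT-proBNP:** they keep about 64% of the information. That figure assumes a roughly normal modifier and a linear interaction; a skewed modifier such as BNP would need a log scale first. Primary power is unaffected.

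Fixing the list and using continuous interaction terms is well supported. Making the adjusted model primary is a preference, since the unadjusted test needs no repair.

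**What to change.** Before unblinding:

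1. Name a short closed list of baseline covariates, for example age, LVEF, diabetes, NYHA class, jeopardy score, creatinine and standardised BNP/NT-proBNP. All but diabetes appear in SAP section 7; diabetes is named as a subgroup variable in section 5.3, so confirm that it is recorded completely. State which LVEF is meant, because protocol section 10.2 has some baseline core-laboratory echocardiograms done soon after randomisation. Specify simple imputation for missing values.
2. Use that list for the adjusted Cox analysis in sections 6.5.5 and 9.1 in place of forward selection. If forward selection stays for the risk score, give its candidates and entry rule. Section 6.5.5 cites section 5.4 for the risk score, which is described in 5.3; correct this.
3. Preferably make the fixed-list model primary and keep the unadjusted model as sensitivity.
4. Test the age, LVEF and log-standardised BNP/NT-proBNP interactions as continuous terms, keeping median splits for display.

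A centre term is optional.

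The cost is SAP wording, plus one line in protocol section 8.3 if the primary model changes. The adjusted hazard ratio is conditional on the covariates, so the report should say so and show the unadjusted estimate beside it.

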6.6 Statistical Analytical Issues

The majority of the data analyses will be performed with Stata® version 17.1 or later. Other statistical software may also be used where Stata® does not provide the relevant statistical method.

7 EVALUATION OF DEMOGRAPHICS, OTHER BASELINE CHARACTERISTICS AND PCI TREATMENT

7.1 General

Continuous variables will be described by the means and standard deviation except for skewed variables which may be described by the median and inter quartile range (IQR). Categorical variables will be described by frequency and percentages in each category by treatment group.

7.2 Demographics

Demographic data collected at baseline include:

- Sex
- Ethnicity Caucasian, Asian, African-Caribbean, Other
- Date of birth (and age)

7.3 Baseline Physical Examination

Patients will be examined at baseline and the following characteristics recorded:

- Height
- Weight
- Body mass index
- Blood pressure (systolic and diastolic)
- Heart rate
- Smoking history
- ECG if performed (atrial fibrillation, heart rate)
- LVEF (echocardiograph: Simpson's biplane) %
- ICD / CRT inserted

7.4 Screening Medical History

The recipient will have the following baseline disease specific characteristics recorded:

- Previous PCI
- Previous CABG
- Previous stroke
- Angina status (CCS grade 0-4)
- NYHA class
- EQ-5D-5L and KCCQ questionnaires
- Jeopardy score
- Viability assessment method (how assessed)
- Blood tests (Hb, Cr, lipids, BNP/NT-proBNP, HbA1C)
- On dialysis

7.5 Medications

All cardiac medications being taken at randomisation will be summarised as frequency and percentage in each category, by treatment group.

7.6 PCI Treatment

The following PCI treatment specific data are recorded and will be summarised:

- Staging and timing of PCI
- Number of lesions/vessels successfully treated, total number of stents used and type
- Circulatory support, VT/VF requiring defibrillation, cardiorespiratory arrest requiring assisted ventilation, prolonged hypotension
- Bleeding (major/minor), access site complications and acute kidney injury
- Jeopardy score (post PCI, change from baseline)
- Aspirin / additional antiplatelet at discharge
- Days in hospital, time in level 2 environment
- Pre PCI troponin, discharge troponin.
- Creatinine (at discharge, change from baseline)

8 EVALUATION OF TREATMENT COMPLIANCE

8.1 Compliance with Study Intervention

There is no time limit from randomisation to PCI. However, it is recommended that index PCI be carried out as close as possible to randomisation (as either a one-stage or two-stage procedure) to minimise the incidence of major adverse cardiovascular events prior to the assigned treatment. Details of the treatment procedure are recorded to determine if the intervention was applied as planned. In addition, both treatment arms are allocated OMT. Cardiac medication at each timepoint after baseline up to 2 years follow-up will be described by frequency and percentage in each category, by treatment group, and compared using a Chi-squared test (or Fisher's exact test if expected numbers are less than 5).

9 EVALUATION OF EFFICACY PARAMETERS

9.1 Analysis of Primary Outcome Variable: All-cause Death or Hospitalisation due to Heart Failure

The primary analysis will be a comparison of the incidence of all-cause death or hospitalisation due to heart failure over all available follow-up between the intervention (treatment with PCI) and control (OMT alone) arms of the trial. An REVIVED SAP

unadjusted time-to-event analysis will be performed on the primary endpoint, with the time to the first event (or censoring) measured from randomisation on an ITT basis. Hazard ratios together with associated confidence intervals will be calculated from the Cox proportional hazards model. A p-value for the treatment difference will be calculated using a likelihood ratio test. The proportionality assumption underlying the Cox model will be assessed via Nelson-Aalen plots by treatment group and by a more formal test comparing treatment hazard ratios across appropriate pre-specified follow-up time bands. If there is clear non-proportionality, comparisons will also be made in early and later follow-up using cut-points at 6 months, 1 year, and 2 years. Cumulative event rates will be calculated and presented using Kaplan-Meier time-to-event curves. As a measure of absolute treatment difference, cumulative event rates based on Kaplan-Meier estimates will be compared at 2 years and a 95% confidence interval for the difference calculated. Losses to follow-up are expected to be minimal and patients will be included up until the time they experience the event or are censored.

A secondary sensitivity analysis will be performed for the primary endpoint using a Cox model adjusted for those risk factors identified in the risk score model developed for subgroup analysis (Section 6.5.5).

9.2 Analysis of Major Secondary Endpoints

Analysis of major secondary outcomes will be based on the ITT population.

9.2.1 LVEF on Echocardiography at 6 Months and 1 Year

Baseline, 6-month and 12-month echocardiograms will be anonymised and submitted to an independent echocardiography core laboratory (at Guy's and St Thomas' Hospital, London, UK), which will determine LVEF using a Simpson's biplane method for evaluation of the major secondary outcome. Anonymised scans were read by core laboratory readers who were blinded to treatment assignment and also the timing of each echo in relation to randomisation.

Where echocardiograms were not performed at precise follow-up intervals (for example, due to restrictions related to the COVID-19 pandemic), echocardiograms recorded between 4 months to 9 months post-randomisation will be considered as the planned 6-month measure, those recorded from 9 months to 24 months post-randomisation will be considered as the planned 1-year measure and the mean (SD) delay from randomisation to each echocardiogram reported. For patients who die a

value of 0% will be imputed for the primary analysis with a secondary sensitivity analysis excluding these patients.

The mean % LVEF at 6 months and 1 year in each treatment group, together with the absolute difference between these measures (and its associated p-value and 95% confidence interval), will be estimated using a linear mixed effects model for repeated measures as described by Frost, Kenward and Fox.¹

This linear mixed model is an extension of a simpler model suggested by White and Thompson as an alternative to the standard analysis of covariance (ANCOVA) model commonly used for the analysis of clinical trials with only a single follow-up measure of the outcome plus a baseline measure. Key features of the White and Thompson model are that the baseline measure is included in the model as an additional outcome that is allowed to be correlated with the follow-up measure, and whose mean is assumed to be the same in both arms of the trial. In the absence of missing data, the White and Thompson model gives identical effect estimates and virtually identical standard errors to the more standard ANCOVA model. Where there are missing data, the White and Thompson approach has the advantage that patients for whom the follow-up measure is present but the baseline measure is missing can be included in the analysis. It also extends naturally to the model proposed by Frost, Kenward and Fox for the situation where there are multiple follow-up measures.

Like the White and Thompson model, this model includes the baseline measure of % LVEF as an additional outcome variable. It includes time in the model as a categorical variable (baseline, 6 months and 1 year), random intercepts, an interaction between time (categorical) and treatment group, and assumes no effect of treatment at baseline (as with the White and Thompson model). The model uses an unstructured variance-covariance matrix, and allows the baseline and follow-up measures of LVEF to be correlated. This type of model has been used previously to analyse clinical trial data.^{3,4} If there were only a single follow-up measure, this model would be equivalent to the White and Thompson model referred to earlier.

It may be necessary to examine % LVEF for transformations to adhere to the assumptions of the linear mixed model or use bootstrapping techniques if a suitable transformation cannot be found.

An analysis of site reported LVEF will also be undertaken as a sensitivity analysis.

